**Secondary Outcome Measures:**

- Incidence of postoperative leakage requiring intervention through 30-day post-operative evaluation period
- Incidence of intraoperative or postoperative blood transfusion within 72 hours of surgery start time
- Hemoglobin difference between preop hemoglobin and hemoglobin on postoperative day #1 as well as difference between hemoglobin at recovery room and postoperative day #1
- Incidence of reported device-related adverse events through 30-day post-operative evaluation period
- Incidence of product malfunction during stapling
- Total hospitalization time
- Postoperative pain level per standard protocol (0-10 VAS scale completed at Recovery room, 6hrs postop and 7am at POD#1)
- Postoperative nausea presence (0-10 scale VAS completed at Recovery room, 6hrs postop and 7am at POD#1)
- Incidence of vomiting: incidence (at least one per patient) per stapler group, total episodes per group and emesis material (bloody or non-bloody)
- Correlation of number of reloads used and specimen lengths and maximum widths as measured by pathology examination
- Correlation of reload color used with observed bleeding and patient's stomach thickness by path exam
- Correlation of outcome parameters with BMI, visceral fat, gender and age
- Need for clipping the staple line prior to completion of the staple line

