### **Steps and Procedures:**

The study will include 60 total consecutive cases, randomized for stapler type: 30 with the AEON™ Endostapler and 30 with Endo GIA™ Reloads with Tri-Staple™ Technology. Surgeries will be performed by [name].

All patients will undergo the standard preoperative evaluation pathway. Patients must sign informed consent for the operation.

All firings with the AEON™ Endostapler will be done with THICK MODE for the purposes of this study and shall conform to the AEON™ Instructions for Use. All firings with the Endo GIA™ Reloads with Tri-Staple™ Technology and Ultra Universal Handle should be done according to the Endo GIA™ Instructions for Use.

To measure incidence and degree of staple line bleeding, a third-party blinded evaluator will be used. No sutures, cautery or clips shall be applied during stapling for staple line bleeding, unless required at surgeon's discretion. Following the last firing, a member of the surgical or nursing team or the research coordinator present for the case will count 10 seconds and then capture images with the laparoscope. If bleeding from the staple line requires control prior to the last firing, an additional image should be captured before applying sutures, cautery, clips, etc. Five pictures will be obtained from each case: the pylorus, distal sleeve near the distal end of the staple line, mid-sleeve at the incisura angularis, proximal sleeve and GEJ near the proximal end of the staple line. These photographs will be sent by the research coordinator to the third-party evaluator either electronically or by mail. The third-party evaluator will be blinded to the device of each case. Upon receipt of photographs, the evaluator will evaluate staple line bleeding according to a provided Bleeding Severity Scale for Laparoscope Images (Appendix A) and record results in the Bleeding Severity Evaluation Sheet (Appendix E).

At the end of each case, the surgical team will fill out the relevant sections of the Data Collection Sheet (Appendix C).

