**Statistics:**

This is an open-label study (since the patient will be blinded and the evaluation for the primary outcome will be done by a third party blinded to the stapler used). Formal sample size calculations were not performed as the purpose of the study is to demonstrate non-inferiority. The number of subjects was chosen based on feasibility and is considered sufficient to meet the study objectives.

Detailed methodology for summary and statistical analyses of the data collected in this study will be documented in the Clinical Study Report. T-test and chi-square test will be used for univariate analysis of continuous and categorical data respectively. Regression analysis may be used to identify the independent effect of several parameters on primary or secondary outcomes if there are statistically significant differences in univariate analysis.

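### The only analysis named for leak, transfusion and malfunction is a chi-square test of difference; with 30 per arm and few events it is undefined or says little, so each needs a risk difference with an interval

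*Combined protocol and SAP*

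**What the plan says.** The combined protocol and SAP covers analysis in its Statistics section. The rule for comparing the arms is "T-test and chi-square test will be used for univariate analysis of continuous and categorical data respectively". No continuity correction, sparse-table alternative, confidence interval or significance level is given, and further methodology is left to the Clinical Study Report.

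On purpose and size, the section says "Formal sample size calculations were not performed as the purpose of the study is to demonstrate non-inferiority" and then "The number of subjects was chosen based on feasibility and is considered sufficient to meet the study objectives". It states no non-inferiority margin. Regression may follow "if there are statistically significant differences in univariate analysis".

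Under Steps and Procedures, the 60 cases are "randomized for stapler type: 30 with the AEON™ Endostapler and 30 with Endo GIA™ Reloads". Secondary Outcome Measures lists several yes/no outcomes. They include "Incidence of postoperative leakage requiring intervention through 30-day post-operative evaluation period", blood transfusion within 72 hours, device-related adverse events and stapler malfunction. No expected rate is given for any of them.

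**The concern.** A test of difference asks whether the data contradict equality. It cannot show that one device is no worse than the other, and a large p-value from a small sample mostly reflects the sample size. These yes/no outcomes carry much of the safety comparison. If they are uncommon, many of the possible results will be 0 versus 0, where chi-square has no value, or a handful of events, where it is rarely significant even when one device is worse.

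The report would then contain either a blank or a non-significant p-value, in a study whose declared purpose is non-inferiority. A reader could take that as reassurance. Nothing in the plan obliges the report to show how large a difference the data leave open.

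**Working it through.** **Inputs from the documents.** 30 patients per arm (Steps and Procedures); withdrawn patients are replaced, so 30 is used without adjustment; chi-square for categorical data (Statistics). There is no planned figure to reproduce, because no sample size calculation was made.

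**Assumptions.** Event rates of 1% to 5%, with larger contrasts added as a check; two-sided 5% significance; uncorrected Pearson chi-square.

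**1. When the statistic exists.** With *a* and *b* events in arms of 30 and *t* = *a* + *b*, the statistic is 60(*a* − *b*)² / [*t*(60 − *t*)]. At *t* = 0 this is 0/0. For a common rate *p*, P(*t* = 0) = (1 − *p*)^60:

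- 1%: 0.99^60 = 0.547
- 2%: 0.98^60 = 0.298
- 5%: 0.95^60 = 0.046

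**2. How often it is significant.** The exact probability is the sum of the two binomial probabilities over all 31 × 31 tables with p < 0.05. Undefined tables count as not significant.

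| True rates | Chi-square significant | Not significant or undefined |
|---|---|---|
| 1% vs 5% | 4.6% | 95.4% |
| 2% vs 6% | 5.9% | 94.1% |
| 5% vs 15% | 26.4% | 73.6% |
| 1% vs 10% | 27.7% | 72.3% |

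For excesses of about 4 points, non-significance is the expected result. For excesses of 9 or 10 points it is still the more likely result, but far from certain.

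**3. Whether chi-square itself misleads.** With equal rates, the same enumeration gives a type I error of 0.03% at 1%, 0.3% at 2%, 2.8% at 5% and 5.4% at 10%. The worst value over common rates from 0.1% to 50% is about 5.5%. There is no material inflation.

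**4. What an interval would show.** The Wilson limits for 0/30 are 0 and *z*²/(30 + *z*²) = 3.8415/33.8415 = 0.1135. Newcombe's limits for *d* = *p*₁ − *p*₂ are

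- lower: *d* − √[(*p*₁ − *l*₁)² + (*u*₂ − *p*₂)²]
- upper: *d* + √[(*u*₁ − *p*₁)² + (*p*₂ − *l*₂)²]

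where *l* and *u* are the Wilson limits in each arm.

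- 0/30 vs 0/30: 0 ± √(0² + 0.1135²), so −11.4 to +11.4 points. Chi-square is undefined.
- 1/30 vs 0/30 (Wilson 0.0059 to 0.1667 in the first arm): lower 0.0333 − √(0.0274² + 0.1135²) = −0.083; upper 0.1667. That is −8.3 to +16.7 points, with chi-square p = 0.31.
- 3/30 vs 0/30 (Wilson 0.0346 to 0.2562): lower 0.1 − √(0.0654² + 0.1135²) = −0.031; upper 0.256. That is −3.1 to +25.6 points, with chi-square p = 0.076.

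The last case shows the issue most clearly: the p-value alone reads as no difference, while the data are compatible with an excess of 25 points.

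**The case against.** The strongest reply is that the low power comes from 30 patients per arm and no choice of test repairs it. That stands. It also disposes of a remedy a reader might reach for, namely requiring Fisher's exact test because expected counts fall below 5 whenever there are 9 or fewer events. Fisher is significant in 0.24% of trials at 1% versus 5% (Pearson 4.6%), and in 5.6% at 1% versus 10% (Pearson 27.7%), so it makes the uninformative result more common.

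Nor is it safe to infer that Pearson would often declare a difference that exact methods reject. For 0/30 versus 4/30, Pearson gives 0.038 and Fisher 0.112. The unconditional exact p-value, using the same Pearson statistic maximised over common rates, is 0.047. For 1/30 versus 6/30 the three values are 0.044, 0.103 and 0.055. Most of the gap is Fisher's conservatism. The plan also does not exclude a continuity correction, which would bring the rejection rates close to Fisher's.

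A second reply is that a 0 versus 0 table does no harm, because the report will simply state no events in either arm. Counts are indeed informative, but without an interval they do not show that a difference of up to 11 points remains open.

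A reader might also infer that the plan will treat p > 0.05 as proof of non-inferiority. No section says so, and none ties the non-inferiority aim to these secondary outcomes; the Summary places the main weight on staple line bleeding. The supportable statement is that the result could be misread. Finally, the rarity of these events is an assumption.

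**Conclusion.** The point holds as a weakness in reporting and interpretation. The plan states a non-inferiority purpose and names only a test of difference for these outcomes, with no interval. At assumed rates of 1% to 5%, that test is undefined in 55% to 5% of trials when the arms are equal. It detects excesses of about 4 points in only 5% to 6% of trials.

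Two stronger readings are not supported. Non-significance is not near-certain whatever the truth, since a contrast of 1% versus 10% is detected 28% of the time. The choice of chi-square is also not the fault. The figures rest on the assumed rates, a two-sided 5% level and an uncorrected statistic; with a correction the power would be lower still. The missing non-inferiority margin is a separate and larger matter, which affects the primary outcome first.

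**What to change.** Add to the Statistics section:

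- For every binary outcome, report the number of events and patients in each arm and the risk difference (AEON minus Endo GIA) with a two-sided 95% Newcombe or score interval. Name the method before data are seen, and give the interval when there are no events as well.
- Base comparative statements on these outcomes on that interval.
- State that a non-significant chi-square result for leak, transfusion, malfunction or device-related adverse events is not evidence of non-inferiority.

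Chi-square can remain as a supplementary p-value, and no change of test is required. This belongs in the plan itself, because methods first set out in the Clinical Study Report are not pre-specified.

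The cost is a few sentences and a few lines of code, with no extra patients or data. The downside is that the intervals will be wide and the safety conclusions less favourable than a row of non-significant p-values would suggest. The interval also does not establish non-inferiority on these outcomes, since no margin is stated.

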**Direct Access to Source Data/Documents:**

The Principal Investigator will ensure that the Sponsor, IRB, and regulatory authorities will have direct access to all study sites, source data/documents, and reports for the purpose of monitoring and auditing. In the event that other study-related monitoring should be done by other parties, those parties will be required to sign a confidentiality agreement prior to any monitoring or auditing.

**Appendix A – Bleeding Severity Scale for Laparoscope Images**

**Bleeding Severity Scale**

**1**

**2**

**3**

[figure not shown]
**4**

[figure not shown]
**5**

## Appendix B – Bleeding Severity Scale for Endoscope Images

### Bleeding Severity Scale

[figure not shown]
1

2

**Appendix B – Bleeding Severity Scale for Endoscope Images (continued)**

[figure not shown]
**Bleeding Severity Scale**

**3**

**4**

**5**

## Appendix C – Data Collection Sheet

Surgery Date: \_\_\_\_\_ Surgeon: \_\_\_\_\_ Hospital: \_\_\_\_\_

Stapler Type (Circle): AEON™ Endostapler Endo GIA™ with Tri-Staple™ Technology

Patient Gender: \_\_\_\_\_ Patient Age: \_\_\_\_\_ Patient BMI: \_\_\_\_\_

AEON™ Endostapler	Black 60mm	Purple 60mm	Purple 45mm	Orange 60mm	Orange 45mm	White 60mm	White 45mm
Quantity Reloads Used							

Endo GIA™ with Tri-Staple™ Technology	Black 60mm	Black 45mm	Purple 60mm	Purple 45mm	Tan 60mm	Tan 45mm
Quantity Reloads Used						

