## **SUMMARY**

The goal of this prospective, post-market study is to measure AEON™ Endostapler performance for laparoscopic bariatric surgery against the Endo GIA™ Reloads with Tri-Staple™ Technology from Medtronic. Stapler performance will be evaluated primarily by incidence and degree of staple line bleeding from endoscopic images, evaluated by a blinded third-party. The study will include 60 total consecutive cases of individuals undergoing a planned laparoscopic sleeve gastrectomy (LSG). The LSG procedure will be performed according to institutional standard-of-care and all subjects will undergo standard preoperative evaluation as well as post-operative care. Relevant data will be collected using the Data Collection sheet which should be filled out following each procedure by a member of the surgical or nursing team.

**Enrollment:** 60 Subjects Meeting Inclusion/Exclusion Criteria

**Investigator Masking:** None (Open Label)

**Primary Outcome Evaluator Masking:** Yes (Surgeon and Device)

**Devices:** AEON™ Endostapler and Endo GIA™ Reloads with Tri-Staple™ Technology and Ultra Universal Handle

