Gastroscopy will be performed, per standard protocol, at the beginning of the case to suction all gastric contents and decompress the stomach as well at the completion of the sleeve gastrectomy. Evaluation for intraluminal bleeding will be performed at the last gastroscopy according to Appendix E. During the last gastroscopy, no suctioning of the gastric contents will be performed until evaluation for bleeding is made and pictures are obtained. The gastroscopy will be performed before any use of clipping at the staple line unless for circumstances judged by the surgeon to be medically necessary to do so before the endoscopy. These instances will also be recorded. Five pictures will be obtained from each case: the pylorus, distal sleeve near the distal end of the staple line, mid-sleeve at the incisura angularis, proximal sleeve and GEJ near the proximal end of the staple line. These photographs will also be sent to the third-party evaluator for evaluation of staple line bleeding according to a provided Bleeding Severity Scale for Endoscope Images (Appendix B). Results will be recorded in the Bleeding Severity Evaluation Sheet (Appendix E).

The determination of laparoscopic and endoscopic staple line bleeding will be based on the picture with the highest bleeding severity score for laparoscopic and endoscopic evaluation separately. Every effort will be made that all pictures prior to any suctioning of the staple line laparoscopically or endoscopically.

All typical post-operative care will continue, including immediate post-operative care prior to hospital discharge as well as the standard post-operative evaluation. A hemoglobin level will be checked at the

recovery room and at 5am on postoperative day #1 per standard protocol. This hemoglobin must be drawn from the upper extremity opposite from the one with the IV running fluids or at the same extremity with the IV running fluids but distal to the IV. For each post-operative period, a member of the surgical or nursing team will fill out the relevant sections of the Data Collection Sheet (Appendix C).

There will be no follow up study data collected after this point, however the patients will continue the standard follow up regimen per the physician's practice.

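### The patient's blind is stated but not protected, and the Data Collection Sheet shows the stapler to whoever enters the pain and nausea scores

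*Combined protocol and SAP*

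**What the plan says.** **Masking.** The Statistics section opens with "This is an open-label study (since the patient will be blinded and the evaluation for the primary outcome" and goes on to the blinded third party. The Summary has two masking lines. Investigator masking is "None (Open Label"), and masking of the primary outcome evaluator is "Yes (Surgeon and Device"). It has no line for the patient. Steps and Procedures adds, for the image reading, "The third-party evaluator will be blinded to the device of each case".

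**The form.** Appendix C carries "Stapler Type (Circle): AEON™ Endostapler Endo GIA™ with Tri-Staple™ Technology" in its header, then a table of reloads used under each brand name. It continues with intraoperative items and then a postoperative block: pain, nausea, hemoglobin, vomiting episodes, hospitalization time and the 72-hour and 30-day items.

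**Who fills it in.** The surgical team completes its part at the end of the case. After that, "For each post-operative period, a member of the surgical or nursing team will fill out the relevant sections of the Data Collection Sheet".

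**The outcomes.** The secondary outcomes include "Postoperative pain level per standard protocol (0-10 VAS scale completed at Recovery room, 6hrs postop and 7am at POD#1"), and nausea on the same scale at the same three times. The Statistics section names the t-test for continuous data.

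**The concern.** Pain and nausea are the most subjective outcomes in this trial. A blinded patient is their main protection in a study where the investigator is openly unmasked. The plan states that blind but describes no procedure behind it: nothing says who must withhold the device from the patient, or until when. The form used for these outcomes also shows the device to the person entering them. A recovery or ward nurse who was not in the operating room could learn the allocation from the form itself.

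If a recorder's or patient's expectation about one stapler shifted the scores by arm, a difference, or the lack of one, could not be read as an effect of the stapler. In a study meant to show non-inferiority, bias in either direction does harm, since it can create a difference or hide one. It cannot be repaired after the data are collected.

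**Working it through.** **1. The masking statements side by side.**

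| Role | Summary | Steps and Procedures | Statistics |
|---|---|---|---|
| Investigator | None | – | Study called open-label |
| Image evaluator | Masked to surgeon and device | Masked to device | Masked |
| Patient | Not listed | No procedure given | Said to be blinded |
| Postoperative recorder | Not listed | Surgical or nursing team, no masking required | – |

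The patient's blind rests on one clause in Statistics. Some pages are not in the text available for review, so the absence of a procedure can be claimed only for the text that is.

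**2. The forms side by side.**

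| Form | Stapler shown? | Case identifier | Outcomes held |
|---|---|---|---|
| Appendix C | Yes, in the header and reload tables | No case number | Pain, nausea, vomiting, hemoglobin, stay, others |
| Appendix D | No | Case number | Specimen length, width, thickness |
| Appendix E | No | Case number | Image bleeding scores (primary outcome) |

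The sponsor already uses forms that identify the case by number without naming the device. Appendix C is the exception, and it holds the subjective outcomes.

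**3. What follows.** The surgical team starts the sheet, and surgical or nursing staff continue it after the operation. Used as laid out, it shows the allocation to whoever enters a pain or nausea score. The documents do not say where the sheet is completed, whether the patient ever sees it, or who marks the scale.

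**4. An illustration of sensitivity.** The plan gives no SD, alpha, margin or power for these outcomes, so it has no figure of its own to reproduce. The only input from the documents is 30 per arm. The SD (2 to 3 points), the biases (0.5 and 1.0 point) and the two-sided 5% level are all assumptions.

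- Standard error of the difference: SE = SD × √(2/30).
- With no true difference, the t statistic (58 df) is noncentral with parameter bias/SE. The error rate is the probability that it exceeds the two-sided 5% critical value, 2.00, in absolute value.

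| SD (assumed) | SE | Error rate, bias 0.5 | Error rate, bias 1.0 |
|---|---|---|---|
| 2 | 0.516 | 15.9% | 47.8% |
| 2.5 | 0.645 | 11.9% | 33.2% |
| 3 | 0.775 | 9.7% | 24.6% |

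These figures show what a bias of that size would do to a t-test. They are not evidence that seeing a form header produces one.

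**The case against.** **Unmasked staff are the declared design.** The Summary says the investigator is not masked and masks only the primary outcome evaluator, so unmasked recording of secondary outcomes does not contradict it. This stands. The inconsistency is narrower: a patient blind that is claimed in Statistics, absent from the Summary and unsupported by any procedure.

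**The route to bias may be weak.** A reader might infer that a nurse fills in the sheet at the bedside, where the patient can see the stapler, and that the patient's blind is therefore broken. The documents do not support that. The instruction says the sheet is completed for each postoperative period and names no place. The scores follow a standard protocol, so they may be copied later from the chart. If the patient marks the scale, an unmasked transcriber has little influence. The recorder may also be someone from the operating room who knows the device anyway, in which case the form adds nothing. All of this stands, and it limits the claim to a risk. The silence on who marks the scale is a gap in itself.

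**Not every item on the sheet is equally exposed.** Hemoglobin is a laboratory value drawn at set times, and vomiting is a count of episodes. This also stands; the point is mainly about pain and nausea.

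**The reach is limited.** The primary outcome is scored by a blinded third party on a form with no stapler field. That stands fully.

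**Conclusion.** The point holds as a low-cost improvement to the secondary outcomes. Two things rest on the text alone: the patient's blind is asserted without support elsewhere in the plan, and Appendix C shows the stapler on the sheet that holds the pain and nausea scores. It follows that the person entering those scores on the sheet can see the allocation, and that the patient's blind is at risk.

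The size of any bias is unknown. The error rates of 10-16% (bias of 0.5 points) and 25-48% (bias of 1.0 point) depend wholly on the assumed biases and the assumed SD, and should be cited only as illustrations. The primary comparison is not affected by this point.

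**What to change.** **Split Appendix C into two pages and add a case number to both**, since the sheet as shown has none.

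- *Operative page:* stapler type, reload counts, intraoperative items and device-related adverse events, which need the device to be known.
- *Postoperative page:* pain, nausea, vomiting, hemoglobin and hospitalization time, with no stapler or reload field, as in Appendices D and E. Where existing staffing allows, recovery or ward staff who have not been told the device complete it.

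**Align the Summary and the Statistics section.** Both should state that the patient is not told the device until the one-month visit is complete.

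**State that the patient marks the pain and nausea scales.** Where the recorder knew the device, report those outcomes as recorded unmasked.

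**Cost.** One form is re-laid out and a few sentences are added. No new staff are needed, because masked recording is asked for only where current staffing permits. There are two pages to link per case, and staff may still learn the device from the operative record, so the change lowers the risk without removing it.

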### **Withdrawal of Subjects:**

Subjects are free to withdraw from the study at any time for any reason. Every effort will be made to determine why any subject withdraws from the study prematurely and this information will be recorded in the Clinical Study Report.

In addition, subjects may be withdrawn from the study by the Principal Investigator in consultation with the Sponsor for the following reasons:

- Adverse event
- Protocol violation
- Loss to follow-up

If a subject withdraws prematurely, all data normally collected by study completion should be collected at the time of premature discontinuation or at the scheduled discharge. All subjects who withdraw from

the study with an ongoing adverse event must be followed until the event is resolved or deemed stable. At the discretion of the PI, additional follow up visits may be done for subject safety.

Withdrawn subjects will be replaced, until 60 subjects complete the study.

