## Appendix E – Bleeding Severity Evaluation Sheet

Evaluation Date: \_\_\_\_\_ Evaluator: \_\_\_\_\_

Case #	Staple Line Image from Laparoscope	Staple line bleeding per Bleeding Severity Scale (choose one):				
		No bleeding	Minimal bleeding	Moderate bleeding	Excessive bleeding	Profuse bleeding
	A. Pylorus	1	2	3	4	5
	B. Distal sleeve near distal end	1	2	3	4	5
	C. Distal sleeve	1	2	3	4	5
	D. Proximal sleeve	1	2	3	4	5
	E. GEJ near proximal end	1	2	3	4	5

Case #	Staple Line Image from Endoscope	Staple line bleeding per Bleeding Severity Scale (choose one):				
		No bleeding	Minimal bleeding	Moderate bleeding	Excessive bleeding	Profuse bleeding
	F. Pylorus	1	2	3	4	5
	G. Distal sleeve near distal end	1	2	3	4	5
	H. Distal sleeve	1	2	3	4	5
	I. Proximal sleeve	1	2	3	4	5
	J. GEJ near proximal end	1	2	3	4	5

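### Appendix C does not link reloads to picture positions, so the planned colour–bleeding correlation rests on case totals, with low power unless the colour mix varies widely between cases

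*Combined protocol and SAP*

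**What the plan says.** The Secondary Outcome Measures include "Correlation of reload color used with observed bleeding", and the same item adds stomach thickness from the pathology examination. The unit of analysis, case or picture position, is not stated.

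The data for this outcome come from three forms:

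- **Appendix C** has a row headed "Quantity Reloads Used" for each stapler, with seven colour-and-length cells for AEON and six for Endo GIA. It has no field for firing order or location. As it appears in the public document, it also has no case number, although Appendices D and E do.
- **Appendix E** scores bleeding from 1 to 5 at named places such as "B. Distal sleeve near distal end" and "D. Proximal sleeve", five per modality.
- **Appendix D** holds one stomach thickness per specimen.

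Under Steps and Procedures, each case's bleeding result is "based on the picture with the highest bleeding severity score for laparoscopic and endoscopic evaluation separately". The trial has "30 with the AEON™ Endostapler and 30 with Endo GIA™ Reloads with Tri-Staple™ Technology". The Statistics section names the t-test, the chi-square test and optional regression. It gives no correlation method, alpha or power, and says "Formal sample size calculations were not performed as the purpose of the study is to demonstrate non-inferiority".

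**The concern.** Bleeding is recorded with its location and reload use without it. In a case where one colour was fired throughout, nothing is lost, because the colour at every position is known. In a mixed-colour case, a high score at the proximal sleeve could belong to any of the colours used, and no planned form settles which.

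Only a between-case comparison is left: do cases with more reloads of one colour have a higher maximum score? It depends on the colour mix differing between cases, and it ignores the contrast between segments of the same staple line. The consequence is limited to one secondary outcome; the randomised comparison of staplers is not affected. The missing link is simple to record at surgery, and the forms as written do not keep it.

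**Working it through.** The plan states no power for this analysis, so there is no figure to reproduce. The check asks what case totals can detect and what position-level data would add.

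**Inputs from the documents.** 60 cases, 30 per stapler; withdrawals are replaced ("Withdrawn subjects will be replaced, until 60 subjects complete the study"); five scored positions per modality on a 1–5 scale; the case result is the maximum.

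**Assumed inputs.** Two-sided alpha 0.05. A latent normal score cut at assumed thresholds into 1–5, with within-case correlation 0.3. A colour effect of 0.5, 0.8 or 1.2 SD. The number of the five positions made with the thicker reload is one of:

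- fixed at 2;
- narrow (1, 2 or 3, with probabilities 0.2, 0.6, 0.2);
- binomial(5, 0.4);
- wide (0 to 5, equally likely).

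Colours are placed along the line either at random or in sequence with one switch point.

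**Step 1: a case-level correlation in general.** By Fisher's z, the r detectable with 80% power is tanh[(1.960 + 0.842)/√(n − 3)].

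- n = 30: tanh(2.802/5.196) = 0.49. Power at r = 0.3 is 36%.
- n = 60: tanh(2.802/7.550) = 0.355. Power at r = 0.3 is 65%.

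The n = 30 row matters most. Table 2 maps AEON orange and AEON purple both to Endo GIA purple, so colour has no common meaning across staplers and the analysis belongs within stapler.

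**Step 2: simulated power (1,500 runs per cell), colours in sequence.** Each cell gives the Spearman correlation of colour count with the case maximum / the position-level score regressed on colour, adjusted for position, with case-clustered standard errors.

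| n | Effect (SD) | Narrow mix | Binomial mix | Wide mix |
|---|---|---|---|---|
| 30 | 0.5 | 7% / 29% | 12% / 38% | 20% / 48% |
| 30 | 0.8 | 10% / 56% | 20% / 75% | 38% / 87% |
| 30 | 1.2 | 13% / 88% | 36% / 98% | 63% / 99.6% |
| 60 | 0.5 | 9% / 46% | 16% / 63% | 35% / 78% |
| 60 | 0.8 | 16% / 84% | 37% / 96% | 67% / 99% |
| 60 | 1.2 | 25% / 99% | 65% / 100% | 92% / 100% |

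Over both colour orders, case-maximum power is 7–15% (n = 30) and 9–25% (n = 60) with a narrow mix, and 20–65% and 34–92% with a wide mix. Using the mean of the five scores instead of the maximum (sequential order) raises case-level power to 9–86% and 10–99% over the varying mixes.

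**Step 3: the limits.** If every case has the same mix, the case-level correlation is undefined. If every case also has the same colour at the same position, colour and position are fully confounded, and position-level data recover nothing either.

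**Step 4: whether a simple within-patient test is safe.** A second model used yes/no bleeding per firing, 60 cases, five firings and 2 or 3 firings of the second colour placed first. It assumed no colour effect and a bleeding gradient along the line. The unadjusted within-patient t-test rejected 16%, 48% and 78% of the time for gradients of 0.25, 0.5 and 0.7 log-odds per unit over a span of two units. A position-adjusted, case-clustered analysis stayed near 5–7%.

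**The case against.** The strongest reply is that the natural reading of the outcome is one value per case. Bleeding is defined by the case maximum, and thickness, which sits in the same item, is one value per specimen. The form supports that reading, and no position-level analysis is promised. This stands: the plan is not contradicted and the correlation can be computed. What remains is that an informative part of the data is lost for want of one field.

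A reader might infer that the planned correlation has almost no power. The documents do not support that, because they give no colour mix, effect size or alpha. In the per-firing model with 60 cases, bleeding of 8% versus 22% by colour, and every case held to 2 or 3 of five firings of one colour, case-level power is about 8% and within-patient power about 93%. Holding the mix that tight removes nearly all the between-case variation. Let it run from 0 to 5 and case-level power is about 40%; restrict the tight mix to one stapler's 30 cases and within-patient power falls to about 65%.

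A reader might also infer that a firing log alone allows a clean within-patient comparison. It does not. Colour is not randomised along the staple line, since product choice is left to the surgeon's judgment, and Step 4 shows the result. Five pictures are also not five firings: they are anatomical views, and the number of firings per case is not specified. The log therefore needs an explicit position field.

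**Conclusion.** The concern holds as a limited design point. Appendix C cannot tie a scored picture to a reload in mixed-colour cases, so the colour–bleeding outcome falls back on case totals. Under the assumed inputs, case-maximum power is about 7–25% with a narrow mix and reaches 65% (n = 30) or 92% (n = 60) only with a wide mix and a 1.2 SD effect. Position-level analysis had higher power than the case maximum in every varying-mix setting tabulated; for example, 75% against 20% at n = 30, 0.8 SD, binomial mix.

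These figures rest on the assumed mix, effect, correlation and score thresholds. The direction is secure; no single power value is. Priority is low: the outcome is secondary, but the remedy is cheap and has to be in place before the cases it is meant to cover.

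**What to change.** 1. Replace the quantity grid in Appendix C with a firing log, one line per firing: firing number from distal to proximal, colour, cartridge length, and the Appendix E picture position or positions covered. Totals by colour and length follow from it.
2. Add the case number to Appendix C so that it joins to Appendices D and E.
3. Reconcile the position labels first. Steps and Procedures describes the third picture as mid-sleeve, but Appendix E labels rows C and H as distal sleeve.
4. State the analysis: position-level score on reload colour, within stapler, by a method suited to an ordinal score, adjusted for position and clustered by case. Do not use an unadjusted within-patient comparison. Keep the case-level correlation as a supporting analysis.

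The cost is one short line per firing on a form the surgical team already completes after each case. If colour always follows position, the log will show it, but no analysis can then separate the two effects.
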